10.4 Reportable Device Issues

Device complaints and device malfunctions will be reported except in the following circumstances. These occurrences are expected and will not be reported on a Device Deficiency Form:

- CGM sensor, transmitter or Pod lasting fewer days than expected per manufacturer
- CGM tape or Pod adherence issues
- Battery lifespan deficiency due to inadequate charging or extensive wireless communication
- Intermittent device component disconnections/communication failures not requiring system replacement or workaround/resolution not specified in user guide/manual.
- Device issues clearly addressed in the user guide manual that do not require additional troubleshooting

10.5 Timing of Event Reporting

SAEs possibly related or related to a study device or study procedures and UADEs must be reported to the Sponsor/CRO within 2 business days of the site becoming aware of the event. This can occur via phone or email, or by completion of the AE eCRF. If the form is not initially completed, it should be completed as soon as possible after there is sufficient information to evaluate the event. All

other reportable AEs should be submitted by completion of the AE eCRF within 5 business days of the site becoming aware of the event.

Each principal investigator is responsible for reporting adverse events required by this protocol and abiding by any other reporting requirements specific to his/her Institutional Review Board or Ethics Committee.

Upon receipt of a UADE report, the Sponsor will investigate the UADE and if indicated, report the results of the investigation to all participating investigators, overseeing IRBs, and the FDA within 10 business days of the Sponsor becoming aware of the UADE per 21CFR 812.46(b). Copies of the associated reports and correspondence with the investigators, regulatory authorities, and Sponsor must be retained with study records.

The Medical Monitor must determine if the UADE presents an unreasonable risk to participants. If so, the Sponsor must ensure that all investigations, or parts of investigations presenting that risk, are terminated as soon as possible but no later than 5 working days after the Medical Monitor makes this determination and no later than 15 working days after first notice of the UADE.

Device deficiencies will be handled by the Sponsor or designee as described below.

If the subject is hospitalized because of or during the course of an SAE, then a copy of the hospital discharge summary must be requested for inclusion with the SAE documentation. In case of death, the investigator must make every effort to obtain a copy of the death certificate to submit to the Sponsor. When submitting copies of documentation, all subject identifying information must be redacted and only the unique subject number will be used to label the forms for identification purposes.

For any event where there is suspicion that the study device is involved, the investigator will return the device for evaluation when possible.

10.6 Stopping Criteria

10.6.1 Participant Discontinuation of Study Participation

In the case of a UADE, the Medical Monitor will determine if the use of the study device will be suspended while the problem is diagnosed. The use of the study device may continue if the Medical Monitor believes the event is explainable, unlikely to reoccur and that it is safe for the subject to continue using the device. Alternately, the Medical Monitor may request the study subject, or all study subjects, to stop using the study device or to only use in Manual Mode. Should all study subjects be required to stop using the study device or to only use in Manual Mode due an UADE, use of the study device or Automated Mode will not be restarted until approval is received from the IRB, DSMB and FDA.

Use of the study device by a participant will be discontinued if any of the following occur:

- The investigator believes it is unsafe for the participant to continue on the intervention. This could be due to the development of a new medical

condition or worsening of an existing condition; or participant behavior contrary to the indications for use of the device that imposes on the participant's safety.

- The participant requests that the treatment be stopped
- Participant pregnancy
- Two distinct episodes of DKA as defined above
- Two distinct severe hypoglycemia events as defined above
- One episode of DKA and one severe hypoglycemia event as defined above

An additional requirement for continued study device use following a single DKA or severe hypoglycemia event will be that (1) the site investigator believes that the event is explainable, unlikely to recur, and that it is safe for the participant to continue to use the system and (2) the Medical Monitor concurs. If the Medical Monitor determines that the occurrence of the event indicates that it is not safe for the participant to continue to use the system, use will be discontinued, and the subject will be withdrawn from the study.

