Through extensive in-silico testing, a proprietary bolus calculator has been developed by Insulet and is embedded in the Omnipod Horizon™ system. The bolus calculator can import CGM and trend as long as the pod has an available CGM value. A 3-month outpatient pivotal trial of Omnipod Horizon™ is currently underway however, it is expected that users will primarily use the system in Automated Mode. This study is designed to evaluate the safety and effectiveness of Omnipod Horizon™ System CGM-informed bolus calculator during Manual Mode operation. These data will supplement the extensive in-silico analysis to support safety and effectiveness of the Omnipod Horizon bolus calculator in clinical use.

Training and operation of the Omnipod Horizon™ System is identical in order to use the product with CGM informed Manual Mode or Automated Mode i.e. it is not possible to disable the Automated Mode functionality and still enable CGM integration. Therefore, this clinical protocol is similar to protocols under IDE G190267 and G190270.

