2 OMNIPOD HORIZON™ SYSTEM STUDY DEVICE OVERVIEW

This study is designed to evaluate the safety and effectiveness of Omnipod Horizon™ System CGM-informed bolus calculator during Manual Mode operation. Manual Mode operation has similar functionality comparable to commercially available standalone pumps such as Omnipod Insulin Management System and Omnipod® DASH and may be chosen by the user when they desire full control of their insulin delivery as opposed to automated insulin delivery offered with Automated Mode. The Omnipod Horizon™ System is described below, however, this study will be restricted to Manual Mode operation ONLY.

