2.1.1 Omnipod Horizon™ Controller (App and Algorithm)

The Omnipod Horizon™ Controller is composed of two parts: the Horizon™ application (“app”) and the model predictive control (MPC) algorithm on the Pod. The MPC algorithm provides insulin micro-boluses once every 5 minutes based upon the predicted glucose over a 60-minute prediction horizon. Optimal post-prandial control will require the user to give meal boluses in the same manner as current pump therapy, but normal operation of the MPC algorithm will compensate for missed meal boluses and mitigate prolonged hyperglycemia. The MPC algorithm uses a control-to-target strategy that attempts to achieve and maintain a set target glucose value, thereby reducing the duration of prolonged hyperglycemia and hypoglycemia. The MPC algorithm resides on the Pod (Pump) component of the Omnipod Horizon™ System (similar to the DASH ACE pump cleared in K191679), as described further below).

The Omnipod Horizon™ app will be the primary user interface and will be used to start and stop a Pod, program basal and bolus calculator settings for Manual Mode as well as program settings specific for Automated Mode (hybrid closed-loop).

Manual Mode

In Manual Mode, the Horizon™ System will function equivalently to the Omnipod® DASH System, which was first cleared under K180045, most recently under K191679. This includes delivering insulin at programmed basal rates and bolus amounts with the option to set temporary basal profiles. The Omnipod Horizon™ Controller will also have the ability to function as a sensor augmented pump in Manual Mode, using sensor glucose data provided by the iCGM to populate the bolus calculator.

Automated Mode

Omnipod Horizon™ CGM-informed Bolus Calculator Protocol

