In Automated Mode, the system will support the use of multiple target glucose values, currently intended to be 110-150 mg/dL at commercialization, in 10 mg/dL increments. The experience for the user will reflect current setup flows whereby the health care provider assists the user to program basal rates, glucose targets and bolus calculator settings. These in turn will inform the MPC algorithm for insulin dosing parameters. The insulin dosing parameters will be adapted over time based on the total daily insulin (TDI) delivered during each Pod use. A temporary hypoglycemia protection mode (Hypo Protect) may be implemented by the user for various time durations during Automated Mode. With Hypo Protect, the algorithm reduces insulin delivery and is intended for use over temporary durations when insulin sensitivity is expected to be higher, such as during exercise.

In this study, participants will be instructed to NOT use Automated Mode. This study will be restricted to Manual Mode operation ONLY.

The Omnipod Horizon™ System will include two apps on a locked-down smartphone (Samsung J3), referred to as Personal Diabetes Manager (PDM): the Horizon™ App and the Dexcom App. The Horizon™ App, which will have a similar interface to the cleared Omnipod® DASH System (K191679), will allow the use of large text, graphics, and on-screen instructions to prompt the user through set-up processes. It will also be used to program the user's custom basal insulin delivery profile, check the Pod status, initiate bolus doses of insulin, make changes to a patient's insulin delivery profile, handle system alerts and alarms, and enter Automated Mode.

The Dexcom App interface is identical to the current app of the interoperable Dexcom G6 Continuous Glucose Monitoring System (K191450) and will provide CGM data, alerts, and alarms to the user.

The Horizon™ App and Dexcom App will not directly communicate with one another. Instead, the iCGM transmitter will communicate EGV (estimated glucose values) directly to the Pod. The Dexcom transmitter number must be entered into the Horizon™ App, and this information is sent to the Pod to allow transmission of EGV. The Pod will pair directly to the transmitter to receive EGV for the algorithm and also sends the EGV back to the Horizon™ App as shown in **Figure 1**.

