After informed consent/assent is obtained, a subject identification number will be issued to uniquely identify each subject. The unique identifier will be used to identify the subject throughout the study and will be used for all source documents and electronic Case Report Forms (eCRFs). If the subject is also participating in

the Omnipod Horizon™ Pivotal Study, they may retain their same subject identification number for both studies.

Inclusion Criteria

Subjects must meet all the following criteria in order to be enrolled in the study:

1. Age at time of consent/assent 2-70 years
2. Subjects aged < 18 years must be living with parent/legal guardian
3. Diagnosed with type 1 diabetes for at least 6 months. Diagnosis is based on investigator's clinical judgment
4. Must be a current Omnipod user, or have used an Omnipod in the past
5. Investigator has confidence that the subject, parent, or legal guardian, can successfully operate all study devices and can adhere to the protocol
6. Willing to use only the following types of Insulin during the study: Humalog, Novolog, Admelog, or Apidra
7. Must be willing to use the Omnipod Horizon™ in Manual Mode only and agree not to use Automated Mode functionality
8. Must be willing to use the Omnipod Horizon™ bolus calculator without a connected CGM for the first 7-days of Manual Mode (Phase 1) while manually entering BG values to deliver boluses
9. Must be willing to use the Omnipod Horizon™ bolus calculator with a connected CGM for the last 7-days of Manual Mode (Phase 2) using the CGM-informed bolus calculator to deliver boluses
10. Willing to wear the system continuously throughout the study
11. For subjects not currently enrolled in the Omnipod Horizon™ Pivotal Study (G190270), A1C <10%
12. Must be willing to use the Dexcom App on the Omnipod Horizon™ PDM as the sole source of Dexcom data (except for the Dexcom Follow App)
13. Able to read and speak English fluently (if subject is a young child then Caregiver must meet the criteria)
14. Willing and able to sign the Informed Consent Form (ICF) and/or has a parent/guardian willing and able to sign the ICF. Assent will be obtained from subjects aged <18 years per State requirements.
15. For subjects aged 2-5.9 years of age, parents or trained caregivers agree to be physically present during the decision and delivery of insulin boluses for this age group, as well as agree to be available for glucose monitoring and treatment during the 4-hour post bolus period.

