- Use the bolus calculator to administer meal boluses for all meals when carbohydrates are consumed as well as to administer correction boluses, when desired. For meal boluses, subjects will estimate the grams of carbohydrates for each meal, enter the carbohydrate estimate into the bolus calculator, check and manually enter their BG value into the bolus calculator and administer their meal bolus. For correction boluses, subjects will check and enter their BG value into the bolus calculator and administer their correction bolus. The timing of the bolus delivery will be per each subject's typical dosing routine.
- Consume meals and snacks of their own choosing.
- Subjects may adjust their basal rates or use advanced features such as Temp Basal and Extended Bolus per usual
- Follow their pre-exercise management such as insulin reduction for meal boluses, consumption of snacks, or adjusting their insulin delivery settings
- Treat themselves per their usual routine if they become hypoglycemic or hyperglycemic or have symptoms of either at any time during the study
- Change their CGM per manufacturer's instructions or sooner if necessary
- Change the Pod at least once every 72 hours
- For subjects aged 2-5.9 years of age, parents or trained caregivers will be instructed that they need to be physically present during the decision and delivery of insulin boluses for this age group, as well as be available for glucose monitoring and treatment during the 4-hour post bolus period.

Subjects and caregivers will be reminded to NOT use the system in Automated Mode for the duration of the 14-day study. Any use of automated mode will be considered a protocol deviation.

Subjects not currently enrolled in the Omnipod Horizon™ Pivotal Study (G190270) will be provided, by the site, information regarding treatment of hypoglycemia and hyperglycemia including sick day management and emergency management of severe hypoglycemia and diabetic ketoacidosis. Instructions will be given to subjects on how to contact clinical study staff 24-hours per day to report any study related problems. Subjects will be encouraged to call the clinical study site at any time with any concerns.

8.1.2 Visit 3

Visit 3 will be conducted either over the telephone or in person at the clinical study site on Day 3 ±1d. This visit will include:

- Review of concomitant medications
- Assessment of adverse events
- Assessment of complaints and/or device deficiencies

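### After an unanticipated adverse device effect, restricting subjects to Manual Mode leaves all permitted use of the tested calculator in place

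*Combined protocol and SAP*

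**What the plan says.** Section 10.6.1 sets out what may follow a UADE. The Medical Monitor decides whether device use is suspended during diagnosis. Use may go on if the Monitor judges the event explained, unlikely to happen again, and continuation safe. Otherwise the Monitor may ask one subject, or all of them, "to stop using the study device or to only use in Manual Mode". If all subjects come under either request, "use of the study device or Automated Mode will not be restarted until approval is received from the IRB, DSMB and FDA".

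On the permitted mode, the protocol is consistent:

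- Section 2: "this study will be restricted to Manual Mode operation ONLY". Section 2.1.1 says the same.
- Section 7.1, inclusion criterion 7: subjects must be willing to use the system "in Manual Mode only and agree not to use Automated Mode functionality".
- Section 8.1.1: "Any use of automated mode will be considered a protocol deviation".

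On where the tested feature runs, section 2.1.1 gives the controller the "ability to function as a sensor augmented pump in Manual Mode, using sensor glucose data provided by the iCGM to populate the bolus calculator". Section 2.1.4 places CGM-based correction boluses in both modes. Sections 8 and 8.2.1 define Phase 2 as Manual Mode with the CGM connected and the Enter CGM button in use.

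**The concern.** An option listed among the responses to a serious device event should reduce exposure to whatever may have caused it. In a trial of automated delivery, falling back to Manual Mode does that. Here Manual Mode is the setting in which the investigational feature is being tested, so the fallback and the test condition are the same.

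Two things are at stake. First, a Monitor who picks this option for a calculator-related event would appear to have acted while permitted calculator use went on unchanged. Unlike the clause on continued use, the option carries no condition about explanation, recurrence or safety. Second, section 10.6.1 would then put no outside approval between the event and further use. Section 11.1 expects children aged 2-5.9 to begin enrolling after the 6-70 group has finished. Nothing in section 10.6.1 would keep them from starting Phase 2 if an event in an older subject had been answered this way.

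**Working it through.** No arithmetic applies. The plan gives no figure on this point, and the question is what each response changes. The check sets section 10.6.1 beside the sections on mode and feature.

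**Step 1: mode before the event.** Manual Mode for every subject, by design (sections 2 and 2.1.1), by eligibility (section 7.1) and by instruction (section 8.1.1).

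**Step 2: where the calculator runs.** In Manual Mode, with the CGM connected, in Phase 2 (sections 2.1.1, 2.1.4, 8 and 8.2.1). So Manual Mode in section 10.6.1 cannot mean without the calculator.

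**Step 3: permitted use under each response.**

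| Response in 10.6.1 | Permitted calculator use afterwards | What the restart rule holds if applied to all subjects |
|---|---|---|
| Continue, on the Monitor's three judgements | Unchanged | Not triggered |
| Suspend or stop the device | None | The study device, once all are required to stop |
| Manual Mode only | Unchanged | Automated Mode only |

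The first and third rows leave the same permitted use. Only the first states conditions.

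**Step 4: the restart rule in the third row.** A restart presupposes that something was stopped. After a Manual Mode request the device has not been stopped, so the words about the study device have nothing to act on. What remains is Automated Mode, which the protocol never allows. One could read the sentence as holding both items after either request, but device use would then need approval just when subjects had been asked to keep using the device in Manual Mode. The reading that pairs each request with its own item is the natural one.

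**Step 5: is there a middle step?** Section 10.6.1 has no wording that withdraws Enter CGM or returns subjects to manual BG entry while they keep the pump. Phase 1, as described in section 8.1.1, is that regimen.

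**The case against.** The strongest reply is that the protection exists elsewhere and in firmer terms. Section 10.5 obliges the Medical Monitor to decide whether a UADE poses an unreasonable risk. If it does, the Sponsor must end the parts of the investigation that carry the risk within 5 working days of that decision and 15 working days of first notice. Phase 2 is such a part. Section 10.6.1 also allows suspension and a full stop, and section 10.6.2 allows study activities to be suspended. The Manual Mode request is discretionary and displaces none of these. An independent physician (section 10.7) is unlikely to choose it for a calculator-related event. Continued use without IRB or FDA approval is in any case an outcome that section 10.6.1 already accepts.

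All of this stands as a limit on the harm. It does not make the option work. The section 10.5 route needs a finding of unreasonable risk, and the Monitor's route in section 10.6.2 is a recommendation to the Sponsor. Continued use is accepted only on stated judgements that the Manual Mode option lacks.

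A second reply is that the option is not wholly empty, because "it is not possible to disable the Automated Mode functionality and still enable CGM integration" (section 1). Subjects could enter Automated Mode off protocol, and for an event that arose that way the instruction and the restart rule have some content. This also stands, and it is why the point is confined to permitted exposure. For that case the option largely repeats a ban already in force.

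**Conclusion.** The wording is wrong for this trial. As a response to a calculator-related UADE, the Manual Mode option leaves all protocol-permitted exposure as it was. If it is used for all subjects, section 10.6.1 then requires no IRB or FDA approval for continued calculator use. The size is minor to moderate: one listed safety response does not work, several others do, and no endpoint or analysis is touched. The conclusion about the restart rule rests on the natural reading in step 4.

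Three stronger readings are tempting but not supported:

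- A reader might infer that subjects are unprotected after a UADE. Sections 10.5, 10.6.1 and 10.6.2 show otherwise.
- A reader might infer that the restart rule never works. After a full stop of all subjects it holds the study device, and with it the calculator.
- A reader might infer from the rule's mention of a DSMB, which the supplied text does not otherwise describe, that no board exists. One may be set up in a document not supplied, so nothing here rests on it.

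No number of affected subjects is given, because the documents state no UADE rate. The old text may have come from the related Horizon protocols that section 1 calls similar, but that is an inference and the point does not need it.

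**What to change.** Change section 10.6.1 in three places:

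1. In both sentences that offer Manual Mode as a response, substitute: *stop using the CGM-informed bolus calculator (Enter CGM) and return to manual BG entry as in Phase 1*.
2. Add that, when this is requested for all subjects, those still in Phase 1 or not yet enrolled do not start Phase 2.
3. Let the restart rule apply to *use of the study device or the CGM-informed bolus calculator*.

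The cost is the rewording of two sentences and one added statement. No visits, procedures or subjects are added, because subjects reach Phase 2 after 7 days of manual BG entry in Phase 1. The one downside is that, if the restriction is ever used, the subjects affected will have a shorter Phase 2 exposure. The clinical report should state this.

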10.6.2 Criteria for Suspending or Stopping Overall Study

Study activities will be suspended if the manufacturer of any component of the investigational study device requires stoppage of device use for safety reasons (e.g. product recall).

The affected study activities may resume if the underlying problem can be corrected by a protocol or system modification that will not invalidate the results obtained prior to suspension.

The study Medical Monitor will review all adverse events that are reported during the study. The Medical Monitor may recommend suspension of study activities or stoppage of the study to the Sponsor if deemed necessary based on the totality of safety data available.

